7.2 Adverse events

7.2.1 Variables

The original verbatim terms used by investigators to identify AEs in the eCRF will be mapped to PTs using the MedDRA dictionary using the latest version at data cutoff. The AE PTs will be then grouped by MedDRA PTs into frequency tables according to primary SOC.

7.2.1.1 *Treatment-emergent adverse events*

The analysis of AEs in Period 2, Period 3 and safety follow-up period is considered analysis of treatment-emergent events, as the i.v. formulation is the investigational treatment.

7.2.1.2 *Adverse events related to study treatment*

An AE will be considered related to the study treatment if the investigator answered 'yes' to the question 'Causal relationship to i.v. selexipag' or if it is missing.

7.2.1.3 *Serious adverse events*

An AE will be considered serious if the investigator answered 'Yes' to the question 'Serious?' or if information is missing.

7.2.1.4 *Adverse events leading to discontinuation of study treatment*

An AE is considered as leading to discontinuation of study treatment if the investigator ticked 'Drug withdrawn' on the question 'Action taken with study treatment'.

7.2.1.5 *Injection site reactions*

Injection site reactions will be collected on a separate eCRF page. Clinically significant injection site reactions will be reported as an AE.

7.2.1.6 *Prostacyclin-associated AEs*

Prostacyclin-associated AEs are AEs associated with the pharmacological action of selexipag that have been observed frequently, in particular during the phase of individualized dose titration. According to selexipag Investigator's Brochure (IB) reference safety information, these PTs include headache, diarrhea, nausea, vomiting, jaw pain, myalgia, pain in the extremity, flushing, and arthralgia.

7.2.1.7 *AEs of special interest based on the Utravi Risk Management Plan*

For completeness, AEs will be analyzed according to the Utravi Risk Management Plan (RMP) important identified or potential risks, using searches of MedDRA PTs provided by Global Drug Safety at the time of database closure. In accordance with the RMP, the following categories will be analyzed:

- Hypotension
- Anemia, decrease in hemoglobin concentration

- Hyperthyroidism
- Major adverse cardiovascular events
- Acute renal failure
- Bleeding events
- Light-dependent non-melanoma skin tumors
- Ophthalmological effects associated to retinal vascular system
- Gastrointestinal disturbances denoting intestinal intussusception (manifested as ileus or obstruction).

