2 STUDY OBJECTIVES

2.1 Primary objective(s)

The primary objective of this study is to assess whether temporary switching from a stable oral dose of selexipag to an i.v. dose of selexipag providing comparable exposure to active metabolite ACT-333679 and switching back to the initial oral dose of selexipag is safe and well tolerated in subjects with stable PAH.

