5.1.10 Premature discontinuation of study treatment

A subject is considered as having prematurely discontinued study treatment if the third i.v. selexipag infusion was not initiated.

The decision to prematurely discontinue i.v. selexipag treatment may be made by the subject, the investigator or Actelion personnel. The main reason and whether discontinuation of i.v. selexipag treatment is the decision of the subject (e.g., tolerability- or efficacy-related), the investigator (e.g., due to pre-specified i.v. selexipag treatment discontinuation criteria, an AE or lack of efficacy), or Actelion (e.g., study terminated) must be documented in the CRF.

A subject has the right to discontinue i.v. selexipag treatment at any time, without any justification, by withdrawal from study treatment only or by withdrawal from any further participation in the study (i.e., premature withdrawal from the study [see Section [8.2](#)]). Although a subject is not obliged to provide his/her reason for prematurely withdrawing from the treatment or the study, it is recommended that the investigator makes a reasonable effort to ascertain the reason(s), while fully respecting the subject's rights.

The investigator must discontinue i.v. selexipag treatment for a given subject if, he/she believes that continued administration would be contrary to the best interests of the subject.

Study-specific criteria for discontinuation of i.v. selexipag treatment are described in Section [5.1.11](#).

A subject who prematurely discontinues i.v. selexipag treatment is to be discontinued from the study. For safety reasons, it is recommended to perform the assessments of Visit 3. The EOS telephone call (Visit 4) must be performed, provided that the subject's consent for this limited participation in the study has not been withdrawn. The assessments that are to be performed at each visit are described in [Table 2](#).

A subject who prematurely discontinues i.v. selexipag treatment and withdraws consent to participate in any further study assessments is considered as withdrawn from the study. Subjects who die or are lost to follow-up are also considered as withdrawn from the study. Withdrawal from the study and follow-up medical care of subjects withdrawn from the study is described in Sections [8.2](#) and [8.4](#), respectively.

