5.4.5.2 Auxiliary medications

Oral Uptravi is collected as a mandatory background drug in the previous and concomitant medication page. Dose changes will be listed with PAH-specific therapies.

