5.5 Study treatment exposure and compliance

i.v. selexipag is considered the only study treatment for this study.

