7 SAFETY VARIABLES

7.1 Overview of safety analyses including subgroup analyses

7.1.1 Overview of safety and tolerability endpoints

Safety endpoints in this study comprise the incidence of AEs and serious AEs (SAEs), discontinuations due to AEs, change and newly occurring abnormalities in vital signs, ECG and clinical laboratory values, as well as change in WHO FC and body weight.

The analysis of safety endpoints in different analysis periods [see [Table 2](#)] is summarized in [Table 7](#) below.

Table 7 Overview of safety and tolerability endpoints and populations in planned analysis periods

Endpoint	SCR (Scr)	1 (S)	2 (ivS)	3&FU (ivS)	1&2 (S)	2&3&FU (ivS)	1&2&3&FU (S, ivS)
Main safety and tolerability endpoints							
AEs and SAEs	✓	✓	✓	✓	✓	✓	✓
Prostacyclin-associated AEs ¹ leading to discontinuation of study drug			✓				
Prostacyclin-associated AEs ¹		✓	✓	✓	✓	✓	✓
Injection site reaction AEs ¹			✓				
PAH related AEs ¹		✓	✓	✓	✓	✓	✓
Other safety and tolerability endpoints							
AEs leading to discontinuation of study drug				✓			
AEs related to study drug as judged by the investigator			✓	✓		✓	✓
Deaths during study							✓
ECG abnormalities, QT prolongation		✓	✓	✓	✓	✓	✓
Marked laboratory abnormalities		✓	✓	✓		✓	✓
Marked blood pressure abnormalities		✓	✓	✓		✓	✓
Change from baseline in WHO functional class ²		✓	✓	✓	✓	✓	✓

Periods connected by an ampersand will be analyzed combined.

All analyses will be run on the S, if S and ivS are identical.

¹ As defined by MedDRA search terms ² By visit analyses

(S) = Safety analysis Set, (ivS) = i.v. Safety analysis set, (Scr) = Screened subject set; AE = adverse event; ECG = electrocardiograph; FU = Safety Follow Up; MedDRA = Medical Dictionary for Regulatory Activities; PAH = pulmonary arterial hypertension; SAE = serious adverse event; SCR = Screening period, WHO = World Health Organization.

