	Visit 3	ddMMyyyy / xxx				

Output: <Output name>, Produced by DATAMAP on ddMMyyyy hh:mm (CET),

SDTM Date: ddMMyyyy

Program: /<folder>/<program_name>.sas

Page x of y

Programming note: Display 'not done' in the result section if a specific physical examination was databased as such.

L_PWDT

ACT-293987

Protocol: AC-065A309

Listing of reasons for premature discontinuation of i.v. selexipag treatment

Analysis Set: i.v. Safety Analysis Set

Country: <country>, Site: <Site number>

Subject number	Status	Reason for discontinuation of i.v. selexipag treatment	Details
1001001	Completed		
1001002	Discontinued	Death	
1001003	Discontinued	Physician decision	xxxxx xxxxxxxxx

Output: <Output name>, Produced by DATAMAP on ddMMMyyyy hh:mm (CET),

SDTM Date: ddMMMyyyy

Program: /<folder>/<program_name>.sas

Page x of y

L_AE

ACT-293987

Protocol: AC-065A309

Listing of <Listing title>

Analysis Set: <Analysis set>

Country: <country>, Site: <Site number>

Subject number	System Organ Class Preferred Term (Reported Term)	Start date/time/Day	End date/time/Day	Duration (days)	Serious	Ser. crit.	Intensity	Concom. trt. given	Action taken i.v. selexipag	Related to i.v. selexipag	Outcome
1001001	xxxxxxxxxxxxxxxxxxxx XXXXXXXXXXXXXXXXXXXX (XXX XXX XXXX)	ddMMyyyy/ hh:mm/xx	ddMMyyyy/ hh:mm/xx	xx	Y	2,3	sev	Y	6	Y	Recovered/ Resolved
1001002	xxxxxxxxxxxxxxxxxxxx XXXXXXXXXXXXXXXXXXXX (XXX XXX XXXX) \$	ddMMyyyy/ hh:mm/xx	ddMMyyyy/ hh:mm/xx	xx	N		mod	N	6	N	Recovering/ Resolving

\$ = Injection site reaction adverse event

Seriousness criteria: 1 Death, 2 Life-threatening, 3 Results in significant disability,

4 Birth defect/congenital anomaly, 5 Required/Prolonged hospitalization,

6 Other medical importance, Action taken with i.v. selexipag: 1 Dose not changed,

2 Dose increased, 3 Dose reduced, 4 Drug interrupted, 5 Drug withdrawn,

6 Not applicable, 7 Unknown

Intensity: mild = Mild, mod = Moderate, sev = Severe

System Organ Classes and Preferred Terms are based on MedDRA version <xx.x>.

Output: <Output name>, Produced by DATAMAP on ddMMyyyy hh:mm (CET),

SDTM Date: ddMMyyyy

Program: /<folder>/<program_name>.sas

Page x of y

L_DTH

ACT-293987

Protocol: AC-065A309

Listing of all deaths

Analysis Set: Safety Analysis Set

Country: <country>, Site: <Site number>

Subject number	Death Date / Time / Day	Primary cause of death (Reported term)
1001002	ddMMyy / hh:mm / xxx	XXXXXXXX (XXXXXXXXXXXXXXXXXXXX)

Preferred Terms are based on MedDRA version <xx.x>.

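### As the SAP defines it, the main endpoint of discontinuation due to prostacyclin-associated AEs cannot record any event after the third infusion, so it says nothing about the switch back to oral selexipag

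*SAP*

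**What the plan says.** The primary objective (Protocol 2.1) covers the temporary switch to i.v. selexipag and also whether "switching back to the initial oral dose of selexipag is safe and well tolerated in subjects with stable PAH".

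Protocol 6.2.2 lists discontinuations due to prostacyclin-associated AEs among five main safety and tolerability endpoints, over Periods 1, 2, 3 and follow-up combined. Protocol 6.2.3 asks for the same endpoint by period, including Period 3 with follow-up. Neither section says what is being discontinued. The protocol synopsis singles out this proportion, in the SAF and the i.v. Safety Set, as addressing the primary objective.

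The SAP supplies the event definition:

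- SAP 7.2.1: "An AE is considered as leading to discontinuation of study treatment if the investigator ticked" *Drug withdrawn* for the action taken with study treatment.
- SAP 5.5: "i.v. selexipag is considered the only study treatment for this study".
- SAP 5.4.5.2: "Oral Uptravi is collected as a mandatory background drug in the previous and concomitant medication page", and "Dose changes will be listed with PAH-specific therapies".
- SAP Appendix E, shell L_AE: the only action-taken key is "Action taken with i.v. selexipag: 1 Dose not changed" and its further codes.

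Protocol 5.1.10 is consistent with this: "A subject is considered as having prematurely discontinued study treatment if the third i.v. selexipag infusion was not initiated". SAP 11.1 declares no change from the protocol's analyses.

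**The concern.** The protocol describes a three-step course: oral, i.v., and oral again. A subject who completes all three infusions, and then cannot stay on the initial Uptravi dose because of a prostacyclin-associated AE, has not tolerated the third step. Under the SAP definition that subject is a non-event in the endpoint the synopsis ties to the primary objective. Tabulating the endpoint over more periods would not help, because the limit lies in the event definition. The extra columns would hold structural zeros.

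At stake is how the headline proportion is read. The study is meant to support regulatory filing and to guide the return to Uptravi (Protocol 1.3.1). A figure labelled as covering the whole study, but able to count only failures of the i.v. step, could be taken as evidence on both switches.

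**Working it through.** **1. The plan's own precision figures.** Inputs: 18 subjects in the i.v. Safety Set, about 20 in the SAF, an expected proportion of at most 10%, and a two-sided 95% Clopper-Pearson interval (Protocol 10.3.4, 10.5). For x events in n, the lower limit is the 0.025 quantile of Beta(x, n−x+1) and the upper limit is the 0.975 quantile of Beta(x+1, n−x). At 2 events:

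- 2/18: 1.4% to 34.7%, matching the stated 35%.
- 2/20: 1.2% to 31.7%, matching the stated 32%.

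The sample-size arithmetic reproduces. The issue is which events the proportion can count.

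**2. Can an event occur after the switch back?** A qualifying AE needs *Drug withdrawn* (SAP 7.2.1). The drug in question is i.v. selexipag only (SAP 5.5). Under Protocol 5.1.10 premature discontinuation requires that the third infusion was not started. Even on the looser SAP wording, an event needs an infusion still running or still due. After the third infusion neither is possible. SAP Table 7 appears to tick prostacyclin-associated AEs "leading to discontinuation of study drug" for one period column only. I do not rely on that column's position, because the definitions lead to the same place without it.

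**3. Time covered.** Taking the third infusion to start about 24 h after the first, the window from the first infusion is about 24 h (third infusion not started) to 24 h + 87 min ≈ 25.5 h (third infusion ended). Periods 1 to 3 last 24 + 36 + 7×24 = 228 h to 24 + 36 + 11×24 = 324 h, before follow-up. The shorter window is 24/324 = 7% to 24/228 = 11% of that.

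**4. Do other displays fill the gap?**

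| Display | Shows | Does not show |
|---|---|---|
| Uptravi exposure table (SAP 5.5.1.2, T_EXP_PO) | Day 3 evening dose, with *Other* and *Not received / missing* rows | Any link to an AE; anything after Day 3 |
| Dose-shift figure (SAP 5.5.1.3) | Individual doses, Days 1 to 3 | The same |
| Listing of PAH-therapy changes (CM_PAH_MOD) | Uptravi stops and dose changes in any period | A count; a link to an AE |
| Prostacyclin-associated AE tables (SAP Tables 7 and 8) | Incidence with CIs, including Period 3 with follow-up | Consequence for Uptravi |
| Study discontinuation table (SAP 5.1.3) | Study withdrawals | A subject who stops Uptravi but finishes follow-up, who counts as a completer (Protocol 8.1) |

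**5. Illustration.** The documents give no rate for Uptravi not resumed, stopped or reduced after the switch back, so the counts below are assumptions. With no i.v. withdrawals and n = 18:

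| Subjects affected after the switch back | Endpoint as defined | If those subjects were counted |
|---|---|---|
| 0 | 0/18 (0 to 18.5%) | 0/18 (0 to 18.5%) |
| 1 | 0/18 (0 to 18.5%) | 5.6% (0.1 to 27.3%) |
| 2 | 0/18 (0 to 18.5%) | 11.1% (1.4 to 34.7%) |
| 3 | 0/18 (0 to 18.5%) | 16.7% (3.6 to 41.4%) |

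The stated 35% bound holds for up to 2 events and fails at 3.

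A second view: suppose the true whole-study rate is 10% and an assumed share f of events falls after the third infusion starts. The chance of reporting 0/18 is (1 − 0.1(1−f))^18, which is 15%, 25%, 40%, 63% and 100% for f = 0, 0.25, 0.5, 0.75 and 1.

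**The case against.** The strongest reply is that the switch back is well covered elsewhere. Discontinuation is one of five main endpoints. AEs and SAEs, prostacyclin-associated AEs and PAH-related AEs are all tabulated for Period 3 with follow-up and for all periods combined. Failure to resume Uptravi on the evening of Day 3, or resumption at another dose, is tabulated, plotted and listed. With about 20 subjects and a descriptive analysis, a careful reader could piece the story together. All of this stands. A reader might infer that a failed return to oral treatment would go unreported; the documents do not support that. What is missing is narrower: a planned count that joins the Uptravi change to the AE.

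A second reply is that such events may be rare. Subjects have been on an unchanged dose for at least 28 days, and Protocol 1.4 says these AEs typically arise during titration. This also stands, and nothing in the documents favours 1 to 3 events over none.

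A third is that the endpoint should not be redefined. The protocol endpoint is discontinuations, and the 7.5% planning reference from the pivotal oral selexipag study concerns leaving that study. Merging dose reductions into the proportion would break that correspondence. I accept this, and the fix keeps reductions apart.

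Finally, the eCRF specification is not among the documents, so action taken with Uptravi may be captured somewhere not shown.

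**Conclusion.** The point holds as a limit of the endpoint's definition. From the end of the third infusion the discontinuation endpoint is structurally zero, although the protocol assigns it to Period 3 and follow-up, the primary objective includes the switch back, and the SAP declares no change. No planned table links Uptravi non-resumption, stopping or reduction to a prostacyclin-associated AE.

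The conclusion rests on SAP 7.2.1 and 5.5 with Protocol 5.1.10, and assumes that the AE page records action on i.v. selexipag only, as shell L_AE shows. The size is unknown. The illustrative difference is 0/18 against 5.6% to 16.7% for 1 to 3 assumed subjects, and it is zero if no such events occur.

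Two stronger inferences should be resisted. The table in step 5 does not show that the reported rate will be wrong, because the event counts are assumed. The precision statement in Protocol 10.5 is not miscalculated.

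The change is worth making: it is cheap and lets the study answer its stated question directly.

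**What to change.** In SAP 7.2.1.4 and output AE_PCDC_PT:

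- Keep the i.v.-withdrawal count. Label it as covering the i.v. step only and state that it cannot occur after the third infusion.
- Add a pre-specified supplementary count for Period 3 and follow-up of subjects with a prostacyclin-associated AE ongoing on the date of the change, on two separate rows: (a) Uptravi not resumed or permanently stopped; (b) Uptravi resumed at, or reduced to, a dose below the initial dose.
- Show a combined row for i.v. withdrawal or (a), counting each subject once. Leave (b) out of it, so that the combined row remains a discontinuation measure.
- Give each row a Clopper-Pearson 95% CI.
- Derive the rows from the Uptravi dosing and concomitant-therapy records (Protocol 5.2.2, 5.2.3), excluding the protocol-mandated interruption. SAP Table 2 starts Period 3 at the actual Day 3 evening intake, so the derivation must also say how a subject who did not resume is placed in a period.
- Record the clarification in SAP Section 11.

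The cost is SAP wording, a derived flag for each row and a few table rows. The downsides are that the reported rate may be higher and that attribution by date is approximate: Protocol 5.2.2 lists dates, dose, route and indication for concomitant therapy but no reason for a change. The table footnote should say so. Only counting changes; no subject's dosing is affected.

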7.2.1.8 PAH-related AEs

PAH-related AEs are AEs that are coded to the following MedDRA (Version 21.0) PTs:

Atrial fibrillation	Lung transplant
Atrial flutter	Pulmonary arterial hypertension
Atrial natriuretic peptide abnormal	Pulmonary arterial pressure abnormal
Atrial natriuretic peptide increased	Pulmonary arterial pressure increased
Acute right ventricular failure	Pulmonary oedema
Cardiac failure	Pulmonary hypertension
Cardiac index decreased	Pulmonary hypertensive crisis
Cardiogenic shock	Right atrial dilatation
Cardiopulmonary failure	Right atrial pressure increased
Chronic right ventricular failure	Right ventricular dysfunction
Cor pulmonale	Right ventricular failure
Cor pulmonale acute	Syncope
Oedema peripheral	Vascular resistance pulmonary increased
Jugular vein distension	

7.2.1.9 Non-serious AEs

For the disclosure of the results to EudraCT and ClinicalTrials.gov, non-serious AEs are defined. A non-serious AE is any AE with the question “Serious?” answered “No” by the investigator.

7.2.2 Analysis

The start date/time of the AE record from the CRF will be used to assign the AE to a study period.

Summary tables will be prepared as described in [Table 8](#) for the periods mentioned in [Table 7](#), except for the screening period.

Summary tables by SOC and PT will display the number and percentages of subjects with at least one AE in the respective primary SOC and at least one AE at the PT level. Summaries will be sorted by descending total frequency of SOCs and PTs and alphabetically in case of ties.

Summary tables by PT will display the number and percentages of subjects with at least one AE in the respective PT. Summaries will be sorted by descending total frequency of PTs and alphabetically in case of ties.

AEs occurring during the Screening period, i.e., prior to first dose of Uptravi on Visit 2 Day 1, will be listed.

Due to the small number of subjects, conservative 95% Clopper-Pearson CIs for the proportions will be computed using exact methods.

All AEs occurring during the study from date of informed consent signature to EOS will be listed.

For any injection site reaction (irrespective of clinical significance), the worst grade, criteria of the injection site reaction, as well as its clinical significance will be summarized. Any AEs associated with clinically significant injection site reactions will be summarized by PT and by maximum intensity in the AE table.

Table 8 Overview of adverse event analyses

Category	Approach
All AEs	
- N (%) of subjects having at least one AE by primary SOC and PT- N (%) of subjects having at least one AE by PT- N (%) of subjects having at least one AE by PT and maximum intensity- Listing
SAEs	
- N (%) of subjects having at least one SAE by PT- Listing
Injection site reaction AEs	
- N(%), grade and diagnosis criteria of injection site reactions- N (%) of subjects having at least one clinically significant injection site reaction by PT and maximum intensity- Listing of PTs and specific details
Prostacyclin-associated AEs	
- N (%) of subjects having at least one prostacyclin associated AE by PT- N % of subjects having at least one prostacyclin associated SAE by PT- N % of subjects having least one prostacyclin associated AE leading to discontinuation of study drug by PT- Listing
AEs of special interest based on the Uptravi RMP	
- N (%) of subjects having at least one AE by RMP category and PT- N % subjects having at least one SAE by RMP category and PT (Listing)- N % least one AE by RMP category leading to discontinuation of study drug by RMP category and PT- Listing
PAH-related AEs	
- N (%) of subjects having at least one event by PT- Listing of events
Any AE leading to discontinuation of study drug	
- N (%) of subjects having at least one event by PT- Listing of events
AEs related to study drug as judged by the investigator	
- N (%) of subjects having at least one event by PT- Listing of events

AE = adverse event; PAH = pulmonary arterial hypertension; PT = Preferred Term; RMP = Risk Management Plan;
SAE = serious adverse event; SOC = System Organ Class.

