2.2 Other objectives

- To evaluate the safety and tolerability of selexipag during each study period.
- To evaluate the PK of selexipag and its active metabolite, ACT-333679, at stable oral dose at steady state and after the switch from selexipag oral to selexipag i.v. in subjects with stable PAH.

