3.1.1 Study periods

The study comprises the following consecutive periods:

Screening period:

Up to 28 days; starts with the signing of the Informed Consent Form (ICF) and ends with first day (Visit 2, Day 1) of Period 1 (Uptravi, pre-treatment period).

Treatment and observation period:

The treatment and observation period includes the following consecutive periods:

- Period 1 (Uptravi, pre-treatment period, in-hospital): 1 day
Starts with intake of the morning dose of Uptravi at Visit 2 Day 1 and ends the following day, before initiation of the first infusion of i.v. selexipag.
- Period 2 (i.v. selexipag, treatment period, in-hospital): 36 hours (3 doses)
Starts in the morning of Visit 2 on Day 2 with the start of the first infusion of i.v. selexipag and ends in the evening of Visit 2 on Day 3 before the evening administration of Uptravi. Note: oral administration of Uptravi is interrupted during the treatment period with i.v. selexipag.

- Period 3 (Uptravi, post-treatment period): 7 to 11 days
Starts in the evening of Visit 2 Day 3 with the oral administration of Uptravi and ends 7 to 11 days later, at Visit 3.

[figure not shown]
Safety Follow-up period:

Starts at the end of Visit 3 and ends 30 to 37 days after the last administration of i.v. selexipag with the End-of-Study (EOS) telephone call (Visit 4).

The visit schedule and protocol-mandated procedures will be performed according to the table of assessments [Table 2] and are described in Section 7.

The overall study design is depicted in Figure 1.

Figure 1 Study design

* 12-hour PK profile after the morning dose.

** For convenience hospitalization may be extended to the night before Day 1 and to the night of Day 3.

D = day; EOS = End-of-Study; IV1–IV3 = dose of i.v. selexipag; V = visit

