10.1.6 Usage of the analysis sets

Subject disposition is described for the Screened Analysis Set. Demographics and baseline characteristics will be reported on the SAF. Safety analyses will be carried out on the SAF and on the i.v. Safety Set. PK analyses will be carried out on the PKS. Subject listings are based on the SAF or Screened Analysis Set as applicable. The following table describes the use of the analysis sets.

Table 4 Reporting periods and corresponding analysis sets.

Reporting period(s)*	Variables	Analysis set
Period 1	Safety and tolerability	SAF
Period 2	Safety and tolerability	i.v. Safety Set
Period 3	Safety and tolerability	i.v. Safety Set
Period 1 and 2	Safety and tolerability	SAF
Period 2 and 3	Safety and tolerability	i.v. Safety Set
Period 1 and 2 and 3	Safety and tolerability	SAF
Period 1 and 2	Pharmacokinetic	SAF, PKS

Follow-up period will be reported together with Period 3.

* If a subject does not take at least one dose of selexipag i.v. they will not be considered as having entered Period 2 (or 3).

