2.3 Analysis periods

The study comprises five analysis periods:

Screening period: This period starts with the signing of the Informed Consent Form and ends with the first day of Period 1 (Visit 2 Day 1).

Period 1 (Uptravi, pre-treatment period, in-hospital): This period starts with intake of the morning dose of Uptravi at Visit 2 Day 1, and ends the following day before initiation of the first infusion of i.v. selexipag.

Period 2 (i.v. selexipag, treatment period, in-hospital): This period starts in the morning of Visit 2 on Day 2 with the start of the first infusion of i.v. selexipag, and ends after approximately 36 hours in the evening of Visit 2 on Day 3 with the resuming of administration of Uptravi at the evening dose.

Period 3 (Uptravi, post-treatment period): This period starts in the evening of Visit 2 Day 3 with the first dose of resumed oral administration of Uptravi, and ends 7 to 11 days later at Visit 3.

Safety follow-up period: This period starts at the end of Visit 3 and ends 30 to 37 days after the last administration of i.v. selexipag with the End-of-Study (EOS) telephone call (Visit 4).

[figure not shown]
A summary of analysis periods is presented in [Table 2](#):

Table 2 Summary of analysis periods

Period	Start	Stop
Screening period	Date/time of first Informed consent form signature	Prior to morning dose of Uptravi at Visit 2 Day 1
Period 1: Uptravi, pre-treatment period	Date/Time of Uptravi morning dose intake at Visit 2 Day 1	Prior to start of first infusion of i.v. selexipag at Visit 2 Day 2
Period 2: i.v. selexipag, treatment period	Start date/time of first infusion of i.v. selexipag at Visit 2 Day 2	Prior to evening dose of Uptravi at Visit 2 Day 3
Period 3: Uptravi, post-treatment period	Date/time of Uptravi evening dose intake at Visit 2 Day 3	Visit 3
Safety follow-up period	After end of Visit 3	End of Study

The study design and flow is shown in Figure 1 below. For details, refer to section 3 and section 7 of the AC-065A309 study protocol [D-17.055].

Figure 1 Study design and flow

* 12-hour PK profile after the morning dose.

** For convenience, hospitalization may be extended to the night before Day 1 and to the night of Day 3.

D = day; EOS = End-of-Study; IV1–IV3 = dose of i.v. selexipag; PK = pharmacokinetic; V = visit.

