<Preferred term 8>	xxx (xx.x)	xx.x, xx.x	xxx (xx.x)	xx.x, xx.x	xxx (xx.x)	xx.x, xx.x
...						

CI = Confidence interval

Preferred Terms are based on MedDRA version <xx.x>.

Output: <Output name>, Produced by DATAMAP on ddMMyyyy hh:mm (CET),

SDTM Date: ddMMyyyy

Program: /<folder>/<program_name>.sas

Page x of y

Programming note: Sort by descending frequency and then alphabetically in the PTs in total. Use the following labels:

Analysis Period	Label in summary table
1	Period 1: Uptravi, pre-treatment period
2	Period 2: i.v. selexipag, treatment period
3&FU	Period 3: Uptravi, post-treatment period including safety follow-up period
1&2	Period 1 & 2: Uptravi, pre-treatment period and i.v. selexipag treatment period combined
2&3&FU	Period 2 & 3: i.v. selexipag, treatment period and Uptravi, post-treatment period including safety follow-up period combined
1&2&3&FU	Period 1 & 2 & 3: All post-baseline periods including safety follow-up period

T_AE_PT_INT

ACT-293987

Protocol: AC-065A309

Incidence of adverse events by preferred term and maximum intensity

Analysis Set: <Analysis set>

Preferred Term Intensity	Uptravi b.i.d. dose		
	200-1000 ug N=xxx n (%)	1200-1600 ug N=xxx n (%)	Total N=xxx n (%)
Subjects with at least one AE			
Mild	xxx (xx.x)	xxx (xx.x)	xxx (xx.x)
Moderate	xxx (xx.x)	xxx (xx.x)	xxx (xx.x)
Severe	xxx (xx.x)	xxx (xx.x)	xxx (xx.x)
Missing	xxx (xx.x)	xxx (xx.x)	xxx (xx.x)
<Preferred term 1>			
Mild	xxx (xx.x)	xxx (xx.x)	xxx (xx.x)
Moderate	xxx (xx.x)	xxx (xx.x)	xxx (xx.x)
Severe	xxx (xx.x)	xxx (xx.x)	xxx (xx.x)
Missing	xxx (xx.x)	xxx (xx.x)	xxx (xx.x)
<Preferred term 2>			
Mild	xxx (xx.x)	xxx (xx.x)	xxx (xx.x)
Moderate	xxx (xx.x)	xxx (xx.x)	xxx (xx.x)
Severe	xxx (xx.x)	xxx (xx.x)	xxx (xx.x)
Missing	xxx (xx.x)	xxx (xx.x)	xxx (xx.x)

The maximum intensity of the AE is shown.

All post-baseline AEs are shown (Period 1 & 2 & 3 including safety follow-up)

Preferred Terms are based on MedDRA version <xx.x>.

Output: <Output name>, Produced by DATAMAP on ddMMMyyyy hh:mm (CET),

SDTM Date: ddMMMyyyy

Program: /<folder>/<program_name>.sas

Page x of y

Programming note: Sort by descending frequency and then alphabetically in the PTs. Show missing category only if it occurred in the data.

T_AEINJ

ACT-293987

Protocol: AC-065A309

Grade and diagnosis criteria of injection site reactions

Analysis Set: i.v. Safety Analysis Set

	Uptravi b.i.d. dose 200-1000 ug N=xxx n (%)	1200-1600 ug N=xxx n (%)	Total N=xxx n (%)

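### AE incidence after the switch back to oral drug is shown only within a window of about 30 days, some 20 times the 36 h i.v. period, and the SAP text and table shell disagree on whether intensity is shown by period

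*SAP*

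**What the plan says.** **Measure.** SAP 7.2.2 assigns each AE to a period by its start date and time. It then counts subjects: "Summary tables by PT will display the number and percentages of subjects with at least one AE in the respective PT". SAP 8.1.1 sets the denominator as the number of subjects in the analysis set and period, not time at risk.

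**Windows.** Protocol 3.1.1 gives "Period 1 (Uptravi, pre-treatment period, in-hospital): 1 day", then "Period 2 (i.v. selexipag, treatment period, in-hospital): 36 hours (3 doses") and "Period 3 (Uptravi, post-treatment period): 7 to 11 days". Safety follow-up "ends 30 to 37 days after the last administration of i.v. selexipag" (SAP 2.3). For reporting, the note to protocol Table 4 says "Follow-up period will be reported together with Period 3". SAP Table 7 and the AE shell labels do the same. SAP Table 4 has a row for Period 3 alone, but no AE shell produces it.

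**Objectives.** The primary objective (protocol 2.1, SAP 3.1) covers the switch to i.v. drug and the switch back. A further objective is "To evaluate the safety and tolerability of selexipag during each study period" (protocol 2.2).

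**Intensity.** SAP 7.2.2 says the Table 8 summaries are prepared for the Table 7 periods, apart from screening. Table 8 includes AEs by PT and maximum intensity. In SAP 12.7.1, however, the title of AE_INT lacks the words *by period* that AE_ALL_SOC carries. The footnote of shell T_AE_PT_INT reads "All post-baseline AEs are shown (Period 1 & 2 & 3 including safety follow-up").

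**The concern.** The study has no control arm, so the subject's own oral periods are the only internal reference for tolerability on i.v. drug. The percentage of subjects with at least one AE rises with the length of observation even when nothing changes clinically. If the return to oral drug is summarized only within a month of follow-up, its percentage cannot be set against that for the 36 h infusion period. An effect of the switch in the first day or two would also be mixed with unrelated events over the following weeks.

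On intensity, a programmer who follows the shell will produce one pooled table. No summary of all AEs would then show whether severe events arose during infusion or later.

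**Working it through.** **The plan's own precision figures.** Protocol 10.5 and SAP 2.5 say the upper 95% bound excludes values above 35% (i.v. Safety Set) and 32% (SAF). Exact Clopper-Pearson limits reproduce this: 2/18 gives 1.4% to 34.7%, and 2/20 gives 1.2% to 31.7%.

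**Window lengths**
- Period 1: 1 day. Period 2: 36 h = 1.5 days.
- Period 3 with follow-up: the last infusion is on Day 3 morning and Period 3 starts that evening, about 0.5 day later. The calendar length is 30 − 0.5 = 29.5 to 37 − 0.5 = 36.5 days.
- Required AE recording ends 30 days after i.v. treatment stops (protocol 9.1.4 and Table 2, note 10), so 29.5 days is the working value.

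**Ratios**
- Period 2 to Period 1: 1.5/1 = 1.5.
- Period 3 with follow-up to Period 2: 29.5/1.5 = 19.7 (calendar maximum 36.5/1.5 = 24.3).
- Period 3 alone would still be 7/1.5 = 4.7 to 11/1.5 = 7.3 times Period 2.

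**Effect of length alone.** The documents give no daily AE rate, so a constant first-event rate *r* per subject-day is assumed and varied. Expected incidence over *d* days is 1 − exp(−*r* × *d*). For *r* = 0.05:
- 1 − exp(−0.05) = 4.9%
- 1 − exp(−0.075) = 7.2%
- 1 − exp(−1.475) = 77%

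| *r* (assumed) | Period 1, 1 d | Period 2, 1.5 d | Period 3 + follow-up, 29.5 d | Same, if 36.5 d |
|---|---|---|---|---|
| 0.02 | 2.0% | 3.0% | 45% | 52% |
| 0.05 | 4.9% | 7.2% | 77% | 84% |
| 0.10 | 9.5% | 13.9% | 95% | 97% |

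A 36 h window after the switch back has *d* = 1.5, so under an unchanged rate its expected value equals that of Period 2.

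**Period 1 against Period 2.** At *r* = 0.05 the expected counts are 20 × 0.049 = 1.0 subject of 20 and 18 × 0.072 = 1.3 of 18. The exact intervals for 2/20 (1.2% to 31.7%) and 3/20 (3.2% to 37.9%) are far wider than this length effect.

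**Is a time-based figure planned elsewhere?** No. Event counts appear only in the disclosure tables (SAP 7.2.2.1, shell T_AE_SOC2). Those are stated not to serve the clinical study report, and they have no period split.

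**The case against.** The case for the plan has several parts.

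- **No comparison is planned.** The analysis is descriptive (SAP 8.2), the stated aim is to evaluate each period, and the merger of Period 3 with follow-up is prespecified in the protocol (6.2.3, Table 4). This stands as far as it goes: no error rate, sample size or test is affected. But description is the study's whole output, and the return to oral drug is named in the primary objective.
- **Layout.** A reader might infer that the percentages stand side by side. They do not: the AE shells print one labelled block per period, with dose groups as columns.
- **Oral versus i.v.** A reader might infer that the tables cannot show whether tolerability changed on i.v. drug. That is too strong, given the 1.5-fold ratio between Periods 1 and 2. Pre-dose to post-dose changes in vital signs and ECG (SAP 7.5.1.3, 7.6.3.1) also do not depend on window length.
- **Intensity.** A reader might infer that the SAP chose to pool intensity, or that a severe AE during infusion could not be told from one weeks later. Neither follows. SAP 7.2.2 says by period, and listing L_AE gives start and end times, intensity and relatedness for each event, which is readable for about 20 subjects. L_AE has no period column, though, whereas L_CM does.
- **The rates are assumed.** This also stands. A constant rate may be wrong, since prostacyclin-associated AEs typically occur during titration (protocol 1.4) and these subjects are on stable doses. The roughly 20-fold window ratio does not depend on that assumption.
- **The remedy is imperfect.** A rate averaged over a month still dilutes an early effect of the switch back. A matched window does not ensure equal ascertainment: the Day 3 night in hospital is optional, and the next scheduled visit is Visit 3.

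**Conclusion.** The point holds in two limited parts.

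1. The AE summary tables cannot describe tolerability of the switch back on a scale comparable with the i.v. period, because the only window for it is about 20 times as long and nothing accounts for time at risk. This rests on the documents' own period lengths. The illustrative incidences (about 5%, 7% and 77% at 0.05 per subject-day) rest on an assumed constant rate.
2. SAP 7.2.2 contradicts the AE_INT title and shell T_AE_PT_INT on whether intensity is by period. If the shell is followed, all-AE intensity by period can be read only from the listing.

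For Period 1 against Period 2, small numbers matter more than window length. The change is worth making for interpretability; the trial's design is unaffected.

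**What to change.** 1. Make output AE_INT and shell T_AE_PT_INT by period, as SAP 7.2.2 already states.
2. In AE_ALL_SOC, SAE_ALL_PT, AE_PC_PT and AE_PAH_PT, add a block for the first 36 h after the Day 3 evening Uptravi dose. Use as denominator the subjects with that intake recorded. The clock time of intake (protocol 5.2.3) and AE onset times (protocol 9.1.4) are collected.
3. Show subject-days by period, with events per 100 subject-days as a supplementary column. This does not replace item 2, because an average over a month dilutes an early effect.
4. Footnote the new block: subjects may have been discharged, so AE ascertainment may be lower than in Period 2, when they are inpatients with seven vital-sign time points on each of Days 2 and 3.

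The cost is SAP wording, shell edits and longer tables. No new data are needed.
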